5.2.2.2. Right censored Data

Not applicable.

5.2.2.3. Visit-specific censored Data

Not applicable.

6. STATISTICAL ANALYSES

Note that standard data derivation rule and stat methods are described in Section 11 and will not be repeated below.

6.1. Demography**6.1.1. Analysis of demographics/baseline characteristics planned in the protocol**

The distribution of subjects enrolled among the study centers will be tabulated as a whole and for each group.

The number of subjects who withdraw from the study will be tabulated by group according to the reason for drop-out.

The number of subjects enrolled into the study as well as the number of subjects excluded from PPS analyses will be tabulated as a whole and for each group.

CONFIDENTIAL116566 (ROTA-083)
Statistical Analysis Plan Amendment 2

The deviations from specifications for age and intervals between study visits will be tabulated by group.

The median, mean, range and standard deviation of age (in weeks) at each HRV vaccine dose will be computed by group. The median, mean and standard deviation of height in centimeter (cm) and weight in kilograms (kg) at Visit 1 will be computed by group. The geographical ancestry and sex composition will be presented.

Summary of co-administered vaccinations (i.e., vaccinations given on the day of each HRV vaccine dose) and intercurrent vaccinations (i.e., vaccinations other than the HRV lyophilized and HRV liquid vaccine administered from birth up to Visit 3, excluding vaccination given on the day of HRV vaccine doses) will be summarized by group for the ES.

For a given subject and a given demographic variable, missing measurements will not be replaced.

6.1.2. Additional considerations

All demography summaries will be generated for the ES. The summary of age, height, weight, race and sex will also be provided for the PPS.

Number and reason for elimination from PPS will be tabulated by group. Since the reasons ‘deviations from specification for age’ and ‘deviations from specifications for interval between study visits’ will be part of this table, no separate table will be generated for these 2 reasons for elimination from PPS.

6.2. Exposure**6.2.1. Analysis of exposure planned in the protocol**

Not applicable.

6.2.2. Additional considerations

The number of doses administered will be tabulated for each group.

6.3. Immunogenicity**6.3.1. Analysis of immunogenicity planned in the protocol**

The primary analysis will be based on the PPS for analysis of immunogenicity. If, in any vaccine group, the percentage of vaccinated subjects with serological results excluded from the PPS for analysis of immunogenicity is 5% or more, a second analysis based on the ES will be performed to complement the PPS analysis.

CONFIDENTIAL116566 (ROTA-083)
Statistical Analysis Plan Amendment 2**6.3.1.1. Within group assessment**

The following calculations will be performed for each group

- For each group, at each time point that anti-rotavirus IgA is measured,
 - GMCs and their 95% CIs will be computed.
 - Seropositivity/seroconversion rates and their exact 95% CI will be computed,
 - The distribution of anti-RV IgA antibody concentrations at Visit 1 and Visit 3 will be displayed using Reverse Cumulative Curves (RCCs).

6.3.1.2. Between groups assessment

- The 95% CI for the ratio of anti-RV IgA antibody GMCs at Visit 3 between the HRV liquid vaccine over the HRV lyophilized vaccine will be computed using an ANCOVA model on the logarithm-transformed concentrations. This model will include the vaccine group and the logarithm of the baseline concentration as covariables. The GMC ratio and their 95% CI will be derived by exponential transformation of the corresponding group contrast in the model (primary objective).
- The asymptotic standardized 95% CI for the difference in seroconversion rate at Visit 3 between the HRV liquid vaccine and HRV lyophilized vaccine will be computed (secondary objective) as described in Section 11.1.

Refer to the Section 3.1 for the success criteria of the primary objective.

6.3.1.2.1. Definitions related with between groups assessment

- A seronegative subject is a subject whose anti-RV IgA antibody concentration is below the clinical meaningful threshold of <20 U/ml*.
- A seropositive subject is a subject whose anti-RV IgA antibody concentration is greater than or equal to the clinical meaningful threshold of 20 U/ml.
- Seroconversion is defined as:
 - *for subjects with a pre-vaccination anti-RV IgA antibody concentration <20 U/mL, seroconversion is achieved when the post-vaccination concentration is ≥ 20 U/mL.*
 - *for subjects with a pre-vaccination anti-RV IgA antibody concentration ≥ 20 U/mL, seroconversion is achieved when the post-vaccination concentration is ≥ 2 times the pre-vaccination concentration.*
- The GMCs calculations are performed by taking the anti-log of the mean of the log concentrations transformations. Antibody concentrations below the technical cut-off (<13 U/ml*) of the assay will be given an arbitrary value of half the cut-off for the purpose of GMC calculation.

CONFIDENTIAL116566 (ROTA-083)
Statistical Analysis Plan Amendment 2

* Note: 20 U/ml corresponds to the clinical meaningful threshold to define seroconversion rate, while 13 U/ml corresponds to technical cut-off of revalidated laboratory assay.

An immunogenicity analysis based on the ES will include all vaccinated subjects for whom immunogenicity data is available. For the immunogenicity measurement, missing or non-evaluable measurements will not be replaced.

6.3.2. Additional considerations

Complementary to the within group assessment of immunogenicity; fold increase from pre-vaccination to one month post-dose 2 of anti-RV antibody concentrations will be computed for each group.

The protocol amendment 3 required an additional condition to be part of the PPS. This condition was to have pre-vaccination anti-RV IgA antibody concentration <20 U/mL. As per request from the Indian Regulatory Authorities (DCGI), the PPS analyses addressing the primary and secondary objectives planned in the protocol amendment 3 will be generated, namely for the PPS limited to subjects with available pre-vaccination anti-RV IgA antibody concentrations <20 U/mL.

- The 95% CI for the ratio of anti-RV IgA antibody GMCs at Visit 3 between the HRV liquid vaccine over the HRV lyophilized vaccine will be computed using an ANOVA model on the logarithm-transformed concentrations. This model will include the vaccine group as covariables. The GMC ratio and their 95% CI will be derived by exponential transformation of the corresponding group contrast in the model (primary objective from protocol amendment 3).
- The asymptotic standardized 95% CI for the difference in seroconversion rate at Visit 3 between the HRV liquid vaccine and HRV lyophilized vaccine will be computed (secondary objective from protocol amendment 3).

6.4. Analysis of safety

The ES will be used for the analysis of safety.

6.4.1. Analysis of safety planned in the protocol**6.4.1.1. Within groups assessment**

The following calculations will be performed for each group:

- The percentage of doses and of subjects reporting at least one symptom (solicited or unsolicited) during the 8-day (Day 1-Day 8) solicited follow-up period will be computed, along with exact 95% CI. The same calculations will be done for symptoms (solicited or unsolicited) rated as grade 3 in intensity, for symptoms (solicited or unsolicited) assessed as causally related to vaccination and for symptoms resulting in medically attended visit.

CONFIDENTIAL116566 (ROTA-083)
Statistical Analysis Plan Amendment 2

- The percentage of doses and of subjects reporting each individual solicited general symptom will be computed, over the 8-day (Day 1-Day 8) solicited follow-up period, post vaccination, along with exact 95% CI. The same calculations will be done for each individual solicited general symptom rated as grade 3 in intensity, for each individual solicited general symptom assessed as causally related to vaccination and for symptoms resulting in medically attended visit.
- The verbatim reports of unsolicited AEs will be reviewed by a physician and the signs and symptoms will be coded according to the Medical Dictionary for Regulatory Activities (MedDRA). Every verbatim term will be matched with the appropriate Preferred Term. The percentage of subjects with unsolicited AEs occurring within 31-day (Day 1-Day 31) follow-up period after any dose with its exact 95% CI will be tabulated by preferred term. Similar tabulation will be done for unsolicited AEs rated as grade 3, for unsolicited AEs with causal relationship to vaccination, for unsolicited AE resulting in medically attended visit and for AEs or SAEs leading to drop out.
- The percentages of subjects who started taking at least one concomitant medication, by type, from Day 1 to Day 8 after vaccinations will be tabulated with exact 95% CI. The percentages of subjects who started taking at least one concomitant medication, by type, during the study period will also be tabulated with exact 95% CI.

SAEs reported during the study period will be described in detail.

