1.2. Rationale for the study and study design

The lyophilized formulation of the HRV vaccine was licensed in India in February 2008. This study will be conducted to generate additional clinical data for the liquid formulation of the HRV vaccine in India, as recommended by New Drug Advisory Committee on Vaccines (NDAC-Vaccines) of Drug Controller General of India (DCGI).

This study will be conducted to evaluate the immunogenicity, reactogenicity and safety of the GSK Biologicals' HRV liquid vaccine compared to the GSK Biologicals' HRV lyophilized vaccine. The study is planned to be conducted in healthy infants aged 6-10 weeks at the time of the first dose. Two oral doses of the study vaccine will be administered to the subjects, according to a 0, 1 month schedule. The blood samples for immunogenicity assessment will be collected from all subjects before the first dose and at one month after the second dose of the vaccine.

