10.8.1. Within groups assessment

The following calculations will be performed for each group:

The percentage of doses and of subjects reporting at least one symptom (solicited or unsolicited) during the 8-day (Day 1-Day 8) solicited follow-up period will be computed, along with exact 95% CI. The same calculations will be done for symptoms (solicited or unsolicited) rated as grade 3 in intensity, for symptoms (solicited or unsolicited) assessed as causally related to vaccination and for symptoms resulting in medically attended visit.

The percentage of doses and of subjects reporting each individual solicited general symptom will be computed, over the 8-day (Day 1-Day 8) solicited follow-up period, post vaccination, along with exact 95% CI. The same calculations will be done for each individual solicited general symptom rated as grade 3 in intensity, for each individual solicited general symptom assessed as causally related to vaccination and for symptoms resulting in medically attended visit.

The verbatim reports of unsolicited AEs will be reviewed by a physician and the signs and symptoms will be coded according to MedDRA. Every verbatim term will be matched with the appropriate Preferred Term. The percentage of subjects with unsolicited AEs occurring within 31-day (Day 1-Day 31) follow-up period after any dose with its exact 95% CI will be tabulated by preferred term. Similar tabulation will be done for unsolicited AEs rated as grade 3, for unsolicited AEs with causal relationship to vaccination, for unsolicited AE resulting in medically attended visit and for AEs or SAEs leading to drop out.

The percentages of subjects who started taking at least one concomitant medication, by type, from Day 1 to Day 8 after vaccinations will be tabulated with exact 95% CI. The percentages of subjects who started taking at least one concomitant medication, by type, during the study period will also be tabulated with exact 95% CI.

SAEs reported during the study period will be described in detail.

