3.2. Secondary objectives

- To assess the immunogenicity of the HRV liquid vaccine and HRV lyophilized vaccine, in terms of seroconversion* rates, one month post dose 2 of HRV vaccine.
 - * *Seroconversion is defined as:*
 - *for subjects with a pre-vaccination anti-RV IgA antibody concentration <20 U/mL, seroconversion is achieved when the post-vaccination concentration is ≥20 U/mL.*
 - *for subjects with a pre-vaccination anti-RV IgA antibody concentration ≥20 U/mL, seroconversion is achieved when the post-vaccination concentration is ≥2 times the pre-vaccination concentration.*
- To assess the reactogenicity of the HRV liquid vaccine and the HRV lyophilized vaccine in terms of solicited adverse events (AEs), during the 8-day (Day 1–Day 8) follow-up period after each vaccination.
- To assess the safety of the HRV liquid vaccine and the HRV lyophilized vaccine in terms of unsolicited AEs, during the 31-day (Day 1–Day 31) follow-up period after each vaccination and serious adverse events (SAEs), during the entire study period.

Refer to Section 4.2 for the definition of the secondary endpoints.

4. ENDPOINTS**4.1. Primary Endpoint**

- Anti-RV IgA antibody concentrations
 - Serum anti-RV IgA antibody concentrations, expressed as GMCs, one month post dose 2 of HRV vaccine.

CONFIDENTIAL116566 (ROTA-083)
Statistical Analysis Plan Amendment 2**4.2. Secondary Endpoints**

- Anti-RV IgA antibody concentrations
 - Anti-RV IgA antibody seroconversion rate, one month post dose 2 of HRV vaccine.
- Solicited general symptoms
 - Occurrence of each type of solicited general symptom within the 8-day (Day1-Day 8) solicited follow-up period, after each dose of HRV vaccine.
- Unsolicited adverse events
 - Occurrence of unsolicited AEs within 31 days (Day 1-Day 31) after any dose of HRV vaccine according to Medical Dictionary for Regulatory Activities (MedDRA) classification.
- Serious adverse events
 - Occurrence of SAEs from dose 1 of HRV vaccine up to study end.

5. ANALYSIS SETS**5.1. Definition****5.1.1. Exposed Set**

The Exposed Set (ES) will include all subjects with at least one study vaccine administration documented.

- A safety analysis based on the ES will include all vaccinated subjects.
- An immunogenicity analysis based on the ES will include all vaccinated subjects for whom immunogenicity data is available.

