10. LIST OF FINAL REPORT TABLES, LISTINGS AND FIGURES (TFL)

The TFL Table Of Content (TOC) is as separate document. It provides the list of tables/listings and figures needed for the study report, and It also identifies the tables eligible for each analysis and their role (synopsis, in-text, post-text, SHS, CTRS).

The following group names will be used in the TFLs, to be in line with the T-domains:

Group order in tables	Group label in tables	Group definition for footnote
1	HRV Liq	HRV liquid vaccine
2	HRV Lyo	HRV lyophilised vaccine

CONFIDENTIAL116566 (ROTA-083)
Statistical Analysis Plan Amendment 2**11. ANNEX 1 STANDARD DATA DERIVATION RULE AND STATISTICAL METHODS****11.1. Statistical Method References**

The exact two-sided 95% CIs for a proportion within a group will be the Clopper-Pearson exact CI [Clopper CJ, Pearson ES. The use of confidence or fiducial limits illustrated in the case of binomial. *Biometrika*. [1934;26:404-413].

The standardised asymptotic two-sided 95% CI for the group difference in proportions is based on the method described in the following paper: Robert G. Newcombe, interval estimation for the difference between independent proportions: comparison of eleven methods, *Statist Med*. 1998; 17, 873-890]. The standardised asymptotic method used is the method six.

The GMC group ratio will be obtained using an ANCOVA model on the logarithm-transformed concentrations. This model will include the vaccine group and the logarithm of the baseline concentration as covariables. The ANCOVA model will include the vaccine group. The GMC ratio and their 95% CI will be derived by exponential transformation of the corresponding group contrast in the model.

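### No between-group contrast is planned for safety or reactogenicity, although the stated purpose is to compare the liquid with the lyophilised vaccine

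*SAP*

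**What the plan says.** - **Purpose.** Protocol 1.2 says the study is "to evaluate the immunogenicity, reactogenicity and safety of the GSK Biologicals' HRV liquid vaccine compared to the GSK Biologicals' HRV lyophilized vaccine". The synopsis gives the same purpose. Infants are randomised 1:1, 225 per arm, to a concurrent active control.
- **Formal objective.** SAP 3.2, like protocol 2.2, is worded without a comparison: "To assess the reactogenicity of the HRV liquid vaccine and the HRV lyophilized vaccine in terms of solicited adverse events (AEs". No safety hypothesis or margin is stated.
- **Safety analysis.** Protocol 10.8.1 and SAP 6.4.1.1 each contain a within-groups section and nothing after it that contrasts the arms. For individual symptoms the SAP, like the protocol, says "The percentage of doses and of subjects reporting each individual solicited general symptom will be computed, over the 8-day (Day 1-Day 8) solicited follow-up period", with an exact 95% CI per group. The results are given per dose and per subject, and again for grade 3, causally related and medically attended symptoms. SAP 6.4.2 adds per-dose tables of unsolicited events and a conditional sensitivity analysis on documented doses, but no contrast.
- **Where differences are planned.** SAP 6.3.1.2 provides one for seroconversion (the sentence begins "The asymptotic standardized 95% CI for the difference in seroconversion rate at Visit 3 between the HRV liquid vaccine and HRV lyophilized vaccine will be"). SAP 11.1 describes the method in general terms: "The standardised asymptotic two-sided 95% CI for the group difference in proportions is based on the method described" in a cited methods paper. SAP 6.3.2 uses it again for seroconversion in initially seronegative infants. In SAP 11.2.6 the line for a percentage difference appears only under immunogenicity.
- **Status.** SAP 7 makes everything outside the primary objective descriptive or exploratory.

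**The concern.** The stated question is how the liquid formulation's reactogenicity compares with the lyophilised one, and randomisation gives an unconfounded estimate of that difference. The solicited events (fever, irritability, diarrhoea, vomiting, loss of appetite, cough or runny nose) are ordinary infant complaints, and routine childhood vaccines are allowed throughout. A percentage in one arm therefore mixes formulation effect with background, and the difference between arms is the quantity that removes the background.

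As planned, the reader gets two one-sample CIs per symptom and no measure of uncertainty on the gap between them. Someone who judges by whether the two intervals overlap is applying a much more lenient standard than a 95% CI for the difference. A moderate excess of, say, diarrhoea or vomiting with the new formulation could then be read as no difference.

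The descriptive label does not explain the omission. Seroconversion is also secondary, also descriptive and also worded as an assessment, yet it gets a difference with a CI.

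**Working it through.** **Plan's own figure.** The documents give no sizing or precision figure for safety. The only one is protocol Table 15, for the GMC ratio. At 35% non-evaluable, n = 225 × 0.65 = 146.25 per arm and SE = 0.790 × √(2/146.25) = 0.0924. Then log10(2)/SE = 0.3010/0.0924 = 3.26, less 1.96 is 1.30, and power is 90.3% (90.1% with the t distribution) against the stated 90%. The table reproduces, but it says nothing about safety.

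**Inputs.** n = 225 per arm (protocol 10.3), taking all randomised infants as vaccinated. Exact Clopper-Pearson CI per arm and standardised asymptotic CI for the difference (SAP 11.1). Comparator symptom rates are my assumption: about 5%, 10%, 20% and 40%.

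**Formulas.**
- Per arm, x events in n: lower limit = Beta quantile(0.025; x, n − x + 1), upper limit = Beta quantile(0.975; x + 1, n − x).
- Difference: I used a score interval. Its limits are the values D that solve |p1 − p2 − D| = 1.96 × √{[q1(1 − q1)/n + q2(1 − q2)/n] × 2n/(2n − 1)}, where q1 and q2 are the maximum-likelihood proportions under q1 − q2 = D. At D = 0 both equal the pooled rate.

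**One threshold in full (20%, 45/225 in the comparator).**
- 63/225 in the liquid arm: pooled rate 108/450 = 0.24, SE = √(2 × 0.24 × 0.76/225 × 450/449) = 0.0403, z = 0.0800/0.0403 = 1.98. The CI excludes zero (0.1 to 15.9 points).
- 62/225: pooled 107/450 = 0.2378, SE = 0.0402, z = 0.0756/0.0402 = 1.88. The CI includes zero.
- The comparator's exact CI is 15.0 to 25.8. The liquid arm's lower limit first passes 25.8 at 72/225 (32.0%), a gap of 12.0 points.

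**All four assumed rates.**

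| Comparator | Its exact 95% CI (%) | Difference CI first excludes 0 | Gap (points), CI | Separate CIs first part | Gap (points) | Ratio of gaps |
|---|---|---|---|---|---|---|
| 11/225 (4.9%) | 2.5–8.6 | 22/225 (9.8%) | 4.9 (0.1 to 10.0) | 29/225 (12.9%) | 8.0 | 18/11 = 1.6 |
| 22/225 (9.8%) | 6.2–14.4 | 36/225 (16.0%) | 6.2 (0.0 to 12.6; lower limit just above 0) | 44/225 (19.6%) | 9.8 | 22/14 = 1.6 |
| 45/225 (20.0%) | 15.0–25.8 | 63/225 (28.0%) | 8.0 (0.1 to 15.9) | 72/225 (32.0%) | 12.0 | 27/18 = 1.5 |
| 90/225 (40.0%) | 33.5–46.7 | 111/225 (49.3%) | 9.3 (0.1 to 18.4) | 121/225 (53.8%) | 13.8 | 31/21 = 1.5 |

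**What falls between the two thresholds.** With 45/225 against 71/225 (20.0% and 31.6%), the separate CIs, 15.0–25.8 and 25.5–38.1, still overlap. The difference is 26/225 = 11.6 points, 95% CI 3.5 to 19.5.

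**Rarer events.** At 4/225 (about 2%), as might apply to grade 3 symptoms, the thresholds are 3.6 points (12/225) and 6.2 points (18/225).

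**Precision the added estimate would have.** With equal observed rates, the difference CI is about ±4.3 points at 5%, ±5.6 at 10% and ±7.4 at 20%.

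**The case against.** The strongest reply is that the plan does what its objectives ask. They assess each vaccine, name no safety comparison, and sit under an explicit descriptive label, and the trial is sized only on the GMC ratio. Per-arm percentages with exact CIs are a coherent way to meet them. That stands. The mismatch is with the rationale and the design, not with the objectives.

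A reader might infer that the randomised comparator goes unused. The documents do not support this. The lyophilised arm is the comparator for the primary GMC ratio and for the seroconversion difference, and its safety rates are tabulated alongside the liquid arm's.

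A reader might also infer that the plan would declare similar safety from overlapping CIs. No passage sets such a rule. A gap of 20.0% against 31.6% would be visible, and anyone with the counts could compute the difference. The overlap figures therefore show how poorly the planned display supports a comparison, not an error the plan commits.

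Two further points stand as limits. The trial is open-label (protocol 5.3) with parent-completed diaries (protocol 5.6.13), and unreported symptoms count as absent (SAP 6.4.2). A difference would thus carry any difference in reporting as well as formulation effect, though so does the side-by-side display. Also, the list of tables is a separate document (SAP 10) that I have not seen. It could include such a contrast, but nothing in the SAP text provides for one.

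**Conclusion.** The point holds as a modest, inexpensive improvement. No between-group safety or reactogenicity contrast is planned, although the study's stated purpose is comparative and a suitable method is already in the SAP. Over assumed comparator rates of about 5% to 40% with 225 per arm, separation of the two exact CIs needs a gap about 1.5 to 1.6 times as large as the gap at which the difference CI excludes zero.

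The sizes depend on the assumed rates, on the full 225 per arm being analysed, and on a reader judging by overlap. The absence of a planned contrast depends on none of these. It would be wrong to conclude that a hypothesis test, a power claim or a formal safety objective is violated, or that any estimate is biased. The primary conclusion is unaffected.

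**What to change.** Add to SAP 6.4.2, which already holds analyses beyond the protocol text: for each of the six solicited general symptoms, any grade and grade 3, per subject over both doses in the Exposed Set, the difference in percentage HRV Liq minus HRV Lyo with its two-sided 95% CI by the SAP 11.1 method. State that these are descriptive under SAP 7 and unadjusted for multiplicity. State beside the table that the trial is open-label with parent-completed diaries. Add a matching safety line to the decimal table in SAP 11.2.6.

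Cost: a few sentences and 6 × 2 = 12 contrasts on data already collected, with no extra subjects. The downside is about a dozen unadjusted CIs. If there were no true differences and coverage were exact, about 12 × 0.05 = 0.6 of them would be expected to exclude zero by chance, so an isolated exclusion should not be over-read.
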